**Table 20: EORTC QLQ-C30 questionnaire scoring**

	Raw score	Analysed Score
Functional scales		
Physical functioning:	$(Q1+Q2+Q3+Q4+Q5)/5$	$(1 - (\text{raw score} - 1) / 3) * 100$
Role functioning:	$(Q6+Q7)/2$	$(1 - (\text{raw score} - 1) / 3) * 100$
Emotional functioning:	$(Q21+Q22+Q23+Q24)/4$	$(1 - (\text{raw score} - 1) / 3) * 100$
Cognitive functioning	$(Q20+Q25)/2$	$(1 - (\text{raw score} - 1) / 3) * 100$
Social functioning	$(Q26+Q27)/2$	$(1 - (\text{raw score} - 1) / 3) * 100$
Global health status:		
Global health status/QOL	$(Q29+Q30)/2$	$((\text{raw score} - 1) / 6) * 100$
Symptom scales/Items:		
Fatigue	$(Q10+Q12+Q18) / 3$	$((\text{raw score} - 1) / 3) * 100$
Nausea and vomiting	$(Q14+Q15) / 2$	$((\text{raw score} - 1) / 3) * 100$
Pain	$(Q9+Q19) / 2$	$((\text{raw score} - 1) / 3) * 100$
Dyspnoea	Q8	$((\text{raw score} - 1) / 3) * 100$
Insomnia	Q11	$((\text{raw score} - 1) / 3) * 100$
Appetite loss	Q13	$((\text{raw score} - 1) / 3) * 100$
Constipation	Q16	$((\text{raw score} - 1) / 3) * 100$
Diarrhoea	Q17	$((\text{raw score} - 1) / 3) * 100$
Financial difficulties	Q28	$((\text{raw score} - 1) / 3) * 100$

Descriptive statistics will be used to summarize the 15 scores values and changes from baseline by time windows on the FAS. Figures will be displayed for scores changes by time windows.

## 16.2. EQ-5D-5L

The EQ-5D-5L contains 1 item for each of 5 dimensions health-related quality of life (mobility, self-care, usual activities, pain or discomfort, and anxiety or depression).

Each dimension has 5 levels: Level 1 indicating no problems, Level 2 indicating slight problems, Level 3 indicating moderate problems, Level 4 indicating severe problems and Level 5 indicating extreme problems.

Descriptive statistics will be used to summarize the scored scales at each time window.

For each dimension, the EQ-5D-5L levels will be also described as dichotomised into 'no problems' (i.e. level 1) and 'problems' (i.e. levels 2 to 5) by time windows.

The EQ-5D-5L VAS records the patient's self-rated health on a vertical visual analogue scale numbered from 0 to 100, where the endpoints are labelled 'The best health you can imagine' (i.e. 100) and 'The worst health you can imagine' (i.e. 0).

Descriptive statistics for EQ-5D-5L VAS values and changes will be tabulated by time windows on the FAS. Figure will be displayed for EQ-5D-5L VAS changes from baseline by time windows.

## 16.3. PGIC

PGIC score will be summarized using descriptive statistics by time windows on the FAS.

## 17. BIOMARKERS ANALYSIS

The relationship between protein levels, mutations and clinical outcomes will be explored.

Descriptive statistics for values and changes from baseline in tumor markers blood CEA and CA19-9 will be tabulated by time windows on the FAS.

The primary endpoint and the corresponding 95% CI will be presented by the microsatellite instability (MSI) status subgroups, CEA subgroups and CA19-9 subgroups as described in section 0. Scatter plots highlighting individual results will display baseline CEA vs baseline CA19-9 Levels, each BOCR being identified differently, on the FAS.

The relationship between changes in blood CEA and CA19-9 and radiographic response to treatment will be investigated. Descriptive statistics for percentage change from baseline to nadir in blood CEA and CA19-9 will be tabulated for each type of response (BOCR) on the FAS. The nadir corresponds to the lowest post-baseline blood CEA value recorded for a patient during the study.

All the blood and tissue biomarkers analyses will be exploratory. They will not be part of the CSR, outside the analysis specified above, but summarized in a separate report under the supervision of translational medicine department.

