i	Visual assessment (General inspection of the eyes, examination of motility and alignment, visual disturbance including diminished central vision, blurred vision or loss of vision) to be performed on site by the investigator. Full ophthalmic examination by ophthalmologist to be performed at EOT and, if clinically indicated during treatment, including best corrected visual acuity for distance testing, slit lamp examination, intraocular pressure and dilated funduscopy with attention to retinal abnormalities, OCT and/or fluorescein angiography as appropriate. A full ophthalmic examination at the 30-day follow up is only required if there was a clinically significant abnormality noted at EOT.
j	Dermatologic examinations are to be performed every 8 weeks from Cycle 1 Day 1 (i.e., on Day 1 of Cycles 3, 5, 7...).
k	ECHO/MUGA scans are to be performed on Cycle 2 Day 1 and Cycle 5 Day 1, then every 12 weeks and EOT
l	Tumor evaluations are to be performed every 6 weeks (\pm 7 days) from first dose for the first 12 weeks, then every 8 weeks (\pm 7 days) until disease progression. The time window allowed for the first tumor assessment (i.e. day 42 from first dose) is +7 days.
m	If a subject discontinues study treatment for reasons other than disease progression, then tumor assessments must be performed (as per local and central review) every 6 weeks (first 12 weeks) then every 8 weeks until the start of new anti-cancer therapy, disease progression, death, lost to follow-up, subject's decision or consent withdrawn.
n	PK samples will be collected during Cycle 1 and Cycle 2 only. On Cycle 1 Day 1 postdose at 2 h (\pm 10 min) and 6 h (\pm 30 min). PK samples will be collected on Cycle 2 Day 1 predose (just prior to dosing) and postdose at 2 h (\pm 10 min). PK blood samples for encorafenib/binimetinib and potentially relevant metabolites will be processed to plasma. PK blood samples for cetuximab will be processed to serum.
o	Optional tumor sample will be requested only for subjects that discontinue study drug treatment due to disease progression.

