8.4.2.2. Tumor markers

Blood samples (10 mL of each) for analysis of tumor markers CEA and CA 19-9 will be collected at screening, predose on day 1 of cycle 1 if more than 72 hours after screening and pre-dose on day 1 of each subsequent cycles, and at the EOT visit (Main study period). This measurement will provide a surrogate marker of response to treatment.

During the Study extension period, blood samples (10 mL of each) for analysis of tumor markers (CEA and CA 19-9) will be collected at pre-dose on day 1 of each cycle, and at the EOT visit, only if as per routine clinical practice.

The analysis of these blood samples will be performed by the local laboratory.

8.4.2.3. *Circulating DNA (ct-DNA)*

ctDNA will be analyzed at baseline in a plasma sample (2 blood samples of 10 mL). *BRAF*^{V600E} mutational status will be explored and compared to the *BRAF*^{V600E} mutational status observed in the local test used for inclusion and for retrospective tumor mutation analysis. In addition to *BRAF*^{V600E}, other cancer genes may be explored in order to identify biomarkers for sensitivity or resistance to treatment.

All blood biomarker analysis will be exploratory and will not be part of the CSR.

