Subjects will be eligible for the study based on identification of a  $BRAF^{V600E}$  mutation in the tumor tissue as determined by local laboratory result obtained at any time prior to Screening. Only polymerase chain reaction (PCR) and next generation sequencing (NGS)-based results will be acceptable. The BRAF mutation status must be confirmed by central laboratory no later than 30 days after the first dose of study treatment. In cases where there is a discordance between local assay and central laboratory results (i.e. either no BRAF mutation identified or not a  $BRAF^{V600E}$  mutation), or if the central laboratory is not able to confirm presence of a  $BRAF^{V600E}$  mutation due to inadequate or poor sample condition or absence of available material within 30 days of initiating study therapy, subjects may only continue treatment if there is no clinical indication of deterioration or disease progression and the Investigator determines that the subject is deriving benefit. In such instances, subjects must be informed that the  $BRAF^{V600E}$  mutation status is unconfirmed and must sign a separate informed consent form (ICF) that includes this information and describes alternative treatment options. Subjects with an unconfirmed  $BRAF^{V600E}$  mutation status will be included in the Full Analysis Set (when they have received at least one dose of study treatment (partial or full), cf. section 7).

Treatment will be administered in 28-day cycles until disease progression, unacceptable toxicity, subject's decision, withdrawal of consent, initiation of subsequent anticancer therapy or death. After discontinuation of study treatment, there will be a 30-day safety follow-up period. Subjects will then enter a survival follow-up period after the completed 30 days safety follow up and will be followed for at least 1 year after the start of study treatment of the last subject enrolled. If a subject discontinues the treatment for a reason other than progressive disease, tumor assessment must be performed (as per local and central review) until the start of new anti-cancer therapy, disease progression, death, lost to follow-up, subject decision or withdrawal consent.

The investigational products in this study are encorafenib and binimetinib in combination with cetuximab. Dose schedule is the following:

- Encorafenib: 300 mg PO (oral capsule 4X 75 mg) QD.
- Binimetinib: 45 mg PO (oral tablet 3X 15 mg) BID.

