#### **Exploratory objectives:**

- To assess the relationship between changes in tumor markers (carcinoembryonic antigen [CEA] and carbohydrate antigen 19-9 [CA19-9]) and radiographic response to treatment.
- To assess *BRAF*V600E status in blood circulating tumor DNA (ctDNA) at baseline.
- To assess the potential predictive significance of the microsatellite instability (MSI) status in subjects with *BRAF*V600E mutant mCRC.
- To assess blood- and tissue-based predictive biomarkers of activity

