### 14.1. PRIMARY ENDPOINT: CONFIRMED ORR BASED ON INVESTIGATOR-ASSESSED TUMOR EVALUATION

#### BOCR

The best overall confirmed response (BOCR) will be derived as per RECIST guideline version 1.1.

Only tumor assessments performed before the start of any further antineoplastic therapies (i.e. any additional secondary antineoplastic medication or anti-cancer surgery or radiotherapy) and not later than 30 days after last study treatment administration will be considered in the assessment of BOCR. Clinical deterioration or clinical progression noted on the end-of-treatment eCRF will not be considered as documented disease progression.

The BOCR for each subject is determined from the sequence of overall (lesion) responses according to the following rules:

- CR: at least two determinations of CR at least 4 weeks apart before progression
- PR: at least two determinations of PR or better at least 4 weeks apart before progression (and not qualifying for a CR)
- SD: at least one SD assessment (or better)  $\geq 6$  weeks after start of treatment (and not qualifying for CR or PR).
- PD: early progression  $\leq 9$  weeks after first study treatment administration (and not qualifying for CR, PR or SD).
- NE = all other cases (i.e. not qualifying for confirmed CR or PR and without SD  $\geq 6$  weeks or early progression  $\leq 9$  weeks after first study treatment administration)

Best overall confirmed response will be summarized, with reasons for having unknown status in Non-Evaluable patients, including:

- No baseline assessment, no measurable disease at baseline
- No post-baseline assessment
- All post-baseline assessments have overall response of “NE”
- New antineoplastic therapy (i.e. any additional secondary antineoplastic medication or anti-cancer surgery or radiotherapy) started before first post-baseline assessment
- Unconfirmed CR, PR or SD with first adequate assessment < 6 weeks Progression >9 weeks after first study treatment administration

The following table, based on Table 3 from the RECIST 1.1 guidelines, summarizes the algorithm describing how Best Overall Confirmed Response (BOCR) is determined from the overall tumor assessments. The order used to determine the BOCR is CR>PR>SD>PD, ignoring visits with missing tumor assessments.

All assessments following an assessment of PD will be excluded from the derivation of BOCR.

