12	SD	PD	SD or PD or NE

Case	Best Overall response		BOCR
	First timepoint	Subsequent timepoint	
			
 
• SD, if SD assessment <math>\geq</math> 6 weeks, i.e. 42 days after date of first administration of study treatment,
 
• otherwise PD if PD assessment <math>\leq</math> 9 weeks, i.e. 63 days after date of first administration of study treatment,
 
• otherwise NE
 

13	SD	NE	SD or NE 
 
• SD, if SD assessment <math>\geq</math> 6 weeks, i.e. 42 days after date of first administration of study treatment,
 
• otherwise NE
 

14	NE, -	SD	SD or NE 
 
• SD, if SD assessment <math>\geq</math> 6 weeks, i.e. 42 days after date of first administration of study treatment,
 
• otherwise NE
 

15	CR, PR, SD	-	SD or NE 
 
• SD, if assessment <math>\geq</math> 6 weeks, i.e. 42 days after date of first administration of study treatment
 
• otherwise NE.
 

16	PD		PD or NE 
 
• PD if PD assessment <math>\leq</math> 9 weeks, i.e. 63 days after date of first administration of study treatment,
 
• otherwise NE
 
 Ignore all assessments after initial overall response of PD.
17	NE	NE	NE Where all assessments are Not evaluable

\* As per Table 3 from RECIST guideline (version 1.1).

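### The only table relating CEA and CA19-9 change to response uses each patient's lowest value during the study, so it mixes any true association with length of sampling

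*SAP*

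**What the plan says.** The first exploratory objective in SAP section 6.2 is "To assess the relationship between changes in tumor markers" (CEA and CA19-9) and radiographic response. SAP section 17 serves it with one descriptive table on the FAS: "percentage change from baseline to nadir in blood CEA and CA19-9 will be tabulated for each type of response (BOCR"). The definition that follows reads: "The nadir corresponds to the lowest post-baseline blood CEA value recorded for a patient during the study". It sets no landmark, common window or cap on the number of samples, and it names CEA only, although the table covers CA19-9 as well.

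Three other rules decide how many values enter each minimum:

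- Sampling. Protocol section 8.4.2.2 has markers drawn at screening, at Cycle 1 Day 1 if needed, then "pre-dose on day 1 of each subsequent cycles, and at the EOT visit (Main study period"). In the extension they are drawn only where that is routine practice.
- Treatment length. SAP section 6.1: "Treatment will be administered in 28-day cycles until disease progression, unacceptable toxicity", among other stopping reasons.
- Response category. SAP section 14.1 requires for a confirmed PR "at least two determinations of PR or better at least 4 weeks apart before progression". For PD, Table 10 requires progression within 9 "weeks, i.e. 63 days after date of first administration of study treatment".

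Section 17 also plans marker changes by time window, but for the whole FAS and not by response. Its scatter plot of the two markers uses baseline values.

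**The concern.** The rows of the table (BOCR) and the number of samples behind each minimum both depend on how long the patient stayed on treatment. Someone who progresses at the first scan has little chance to record a low value; someone treated for eight months has many. Even if the marker behaved identically in every patient, the long-treated rows would show deeper falls.

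At stake is the reading of the one planned analysis that sets marker change against response. Section 17 keeps it in the clinical study report, while most other biomarker work goes to a separate report. A reader who sees falls deepen from PD through SD to PR and CR would naturally credit the marker, and nothing in the table shows how much of that pattern is length of sampling.

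**Working it through.** The plan states no figure for this table, so there is none to reproduce. The check has three steps.

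**1. Samples per response category.** Day 1 of cycle c falls on study day 28(c − 1) + 1, that is days 29, 57, 85 and so on. Scans follow the protocol flow-chart ("Tumor evaluations are to be performed every 6 weeks" for 12 weeks, then every 8 weeks), so the first two fall at about days 42 and 84.

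- BOCR = PD. Progression at day 42: day 29 plus EOT = 2 samples. At day 63, the latest allowed: days 29 and 57 plus EOT = 3.
- Confirmed CR or PR. The second scan is at about day 84. Treatment to day 84: days 29 and 57 plus EOT = 3. To day 85: one more = 4. These are minima.
- A long-treated patient. Protocol section 1.3 cites a median of 7.9 months on the triplet in previously treated patients. 7.9 × 30.4375 = day 240, giving 8 cycle samples, or 9 with EOT.
- NE has no upper limit. A first assessment of PD after day 63 is NE under Table 10, so this row mixes short and long sampling.

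**2. Size of the artefact with no marker change at all.** Let the baseline and k later log-values be independent normal with SD σ, the same for every patient. The median change to nadir is 100 × [exp(σ·m_k) − 1], where m_k is the median of (minimum of k standard normals − one further standard normal). Numerical integration gives m_1 = 0, m_2 = −0.5565, m_3 = −0.8368, m_5 = −1.1526 and m_9 = −1.4748. σ is assumed.

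| Samples k | σ = 0.2 | σ = 0.3 |
|---|---|---|
| 1 | 0.0% | 0.0% |
| 2 | −10.5% | −15.4% |
| 3 | −15.4% | −22.2% |
| 5 | −20.6% | −29.2% |
| 9 | −25.5% | −35.8% |

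Example: k = 9, σ = 0.3 gives exp(0.3 × −1.4748) − 1 = −35.8%. Between 2 and 9 samples the spurious gap is 15.0 points at σ = 0.2 and 20.4 points at σ = 0.3. A simulation of 200,000 patients per cell over within-patient CVs from 10% to 50% gives gaps of about 8 points (−5.4% against −13.7%) to about 27 points (−23.1% against −50.3%).

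If instead every patient shares one true course (a 20% fall per cycle, flat from the sixth sample, CV 20%), the simulated medians with 2, 3, 5 and 9 samples are −38.0%, −50.5%, −68.3% and −78.6%. Again the rows differ only in length of sampling.

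**3. What a fixed visit does.** One value per patient is the k = 1 row: 0% in every response group when nothing changes, whatever σ is. SAP Table 7 already defines a Cycle 2 Day 1 window for both markers (day 1 post-dose to day 43), and SAP section 9.3 keeps the value nearest the planned visit when there are several.

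**The case against.** The best case for the plan is that the objective asks about a relationship and not about prediction. BOCR is itself a best-over-time measure, and pairing best marker change with best response follows the same convention as the waterfall plot in SAP section 14.2.11. Section 8 of the SAP treats everything except the primary test as exploratory; no test, threshold or decision uses this table. Within-patient variability is not given, so the figures above are illustrative.

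Most of that stands, and it rules out some stronger readings that a reader might infer:

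- That the table cannot answer its question, or fails because a nadir is not an independent predictor. The documents claim only a descriptive association and no prediction. A real association may be present; the table cannot separate it from length of sampling.
- That PD and NE patients give only one or two samples. With EOT counted, PD gives 2 to 3 and NE is unbounded, so the one-sample figure of 0% is not a fair anchor for those rows.
- That every pair of rows is badly distorted. SD patients may be treated nearly as long as responders; 5 against 9 samples at σ = 0.2 differs by 4.9 points.
- That the nadir runs over the whole study. Scheduled sampling ends at EOT, so in practice it runs over treatment.

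What the objection does not remove is the mechanism. A minimum over more values can only be equal or lower, and the category rules tie the number of values to the row. The by-window summary does not help as planned, because it is not split by response.

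**Conclusion.** The point holds as a minor one. As written, the table builds part of any marker-response gradient from unequal numbers of samples. The direction follows from the definitions alone. The size depends on an assumed within-patient variability and on how long patients are treated: about 5 to 7 points between 2 and 3 samples and 15 to 20 points between 2 and 9, for σ of 0.2 to 0.3 and no true change. The count of 9 rests on treatment time in an external, previously treated population. The artefact would vanish only without measurement noise and with every patient at nadir by the first samples. The primary endpoint and the two-stage decision are unaffected.

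**What to change.** In SAP section 17:

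- Make percentage change from baseline in the existing Cycle 2 Day 1 window, by BOCR, the main table for CEA and for CA19-9, and show the number of patients with a value in each BOCR group.
- Keep the nadir as a listing or secondary table, with the number of samples per BOCR group beside it, and word its definition to cover CA19-9 as well as CEA.

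Two nearby choices should not serve as the main comparison. A nadir limited to the first 12 weeks still leaves a patient who progresses at the day-42 scan with one sample, or two with EOT, against two or three for a responder; at σ = 0.3, two against three is −15.4% against −22.2%. Cycle 3 Day 1 (day 57) loses those patients, because samples after the last dose belong to the safety follow-up window.

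The cost is one sentence and one table, with no new data. The downside is that falls after Cycle 2 Day 1 are not captured in the main comparison and appear only in the secondary nadir display.

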## 18. HEALTHCARE RESOURCE UTILIZATION

Descriptive statistics of hospitalizations occurring during the treatment period (i.e. from first treatment administration date up to last administration date + 30 days included) will be provided.

The number of patients hospitalized, the number of hospitalizations by patient, the cumulative duration of hospitalization by patient, the total number and duration of hospitalizations, the facility used and hospital discharge disposition will be summarized descriptively on the FAS.

For hospitalization that are “ongoing” at the cut-off date, the end date will be imputed to the last contact date to compute the duration.

## 19. PHARMACOKINETICS ANALYSIS

Blood samples for encorafenib, binimetinib and the active metabolite of binimetinib (AR00426032) plasma concentration measurements will be performed as follow:

	Cycle 1 Day 1		Cycle 2 Day 1	
Time after encorafenib/ binimetinib dosing on designated dosing days (h)	2	6	0 (Pre-dose)	2
PK sample for encorafenib, binimetinib and AR00426032	x	x	x	x

Abbreviations: h = hours; PK = pharmacokinetic

PK samples will be collected on Cycle 1 Day 1 postdose (encorafenib/binimetinib) at 2 h (± 10 min) and 6 h (± 30 min). PK samples will be collected on Cycle 2 Day 1 predose (just prior to encorafenib/binimetinib dose) and postdose at 2 h (± 10 min). Blood samples for encorafenib/binimetinib PK will be processed to collect plasma.

Blood samples for serum Cetuximab concentration measurements will be performed as follow:

	Cycle 1 Day 1		Cycle 2 Day 1	
Time after the start of cetuximab infusion on designated dosing days (h)	2	6	0 (Pre-infusion)	2
PK sample for cetuximab	x	x	x	x

Abbreviations: h = hours; PK = pharmacokinetic

PK samples will be collected on Cycle 1 Day 1 post-infusion (cetuximab) at 2 h (± 10 min) and 6 h (± 30 min). PK samples will be collected on Cycle 2 Day 1 pre-infusion (just prior to infusion of cetuximab) and post-infusion at 2 h (± 10 min). Blood samples for cetuximab PK will be processed to obtain serum. Time points are based on the start of infusion.

The pharmacokinetic set (cf section 7) will be used to perform the PK analysis.

